The two youngest affected males are approaching or are in early puberty and the remaining time for further growth is limited. We hypothesize that an alternative approach to improve their growth could be treating them with recombinant human IGF-1 (rhIGF-1, Increlex®), which is FDA-approved in the United States for the treatment of severe primary IGF-1 deficiency. Patients with severe primary IGF-1 deficiency often have GH resistance due to a defect in the GH receptor. These patients also have low free IGF-I concentrations. Long-term treatment with recombinant human IGF-1 has shown to improve these patients' adult height. Therefore, we hypothesize that the administration of recombinant human IGF-1 to patients with PAPP-A2 mutation will result in an increase in the levels of free IGF-1 concentration and hence increase in linear growth.

## 2. Hypothesis and Specific Aims.

### **General Hypothesis**

Treatment with subcutaneous injection of recombinant human IGF-1 in patients with short stature secondary to PAPP-A2 deficiency will increase height velocity.

### **Specific Aims**

- a. Determine the pharmacokinetic parameters of a single SC injection of rhIGF-1 concentration in patients with the PAPP-A2 mutation.
- b. Describe the effects of one year of treatment with rhIGF-1 administered via subcutaneous injection in patients with PAPP-A2 mutation. If the treatment is well-tolerated, treatment will continue until adult height is achieved.
- c. Assess the PK/PD relationship (PD marker being IGFBP-3) during the one year of treatment
- d. Describe additional phenotypic features of patients with PAPP-A2 deficiency including glucose handling, body composition, bone geometry and bone density.
- e. Monitor and quantify the potential development of antibodies to administered rhIGF-1 over a period of 1 year treatment.

## 3. Preliminary Results.

**Treatment with rhIGF-1:** Our colleague [name] from Madrid, Spain is currently executing a similar clinical trial in which two young siblings (male and female) with PAPP-A2 mutation have been receiving twice daily SC rhIGF-1 treatment. The preliminary results show a favorable response in linear growth of both affected individuals.

**Pharmacokinetic study:** [name] Höglér and colleagues have recently published a well-designed pharmacokinetic study that describes free and total IGF-1 response to a single dose of rhIGF-1 in patients with IGF acid labile subunit (ALS) deficiency caused by IGFALS mutations. These patients have similar physiology to patients with PAPP-A2 mutations as ALS prolongs the half-life of circulating IGF-1, and mutations in *IGFALS* result in decreased free IGF-1 levels. However, there are important distinctions between the two conditions due to the different pathophysiological mechanisms. As part of our study, we intend to mimic their protocol by applying it to patients with a PAPP-A2 mutation, which will allow for future comparison of our results to those of the ALS patients. We are already collaborating with [name], one of the co-authors on the ALS manuscript, who performed all of the free IGF-1 assays.

## 4. Study Design and Methods.

Our study is divided in to three different parts:

- 24-hour pharmacokinetic response of free and total IGF-1 and IGF binding protein-3 (IGFBP-3) to a single dose of rhIGF-1 (120 mcg/kg) in three patients with PAPP-A2 mutation compared to up to four unaffected heterozygous relatives and 2 healthy adult controls. This part is complete.

- One-year trial of rhIGF-1 at standard dose given to the two youngest males with PAPP-A2 mutation. The primary end point of this trial will be first year height velocity. Secondary outcomes will include change in height SDS, change in height velocity SDS, and change in whole body and lumbar spine bone mineral density. This part is complete, and will be followed by an extension part. Provided continued improved height velocity (defined as height velocity at the 25th percentile or better) without adverse effects, treatment with IGF-1 will be continued on an annual basis until closure of the growth plates indicating achievement of near-adult or adult height (bone age  $\geq$  15 years or 17 years, respectively, for males).

- Description of additional phenotypic characteristics of patients with PAPP-A2 mutation by studying glucose and insulin metabolism, body composition, bone geometry and bone density before and after treatment with rhIGF-1. This part will be complete in 2019 for the subjects not on Increlex.

#### *4.1. PK response to rhIGF-1:*

The primary objective of this study is to determine the pharmacokinetic (PK) effect of a single injection of rhIGF-1 in patients with PAPP-A2 mutations compared to heterozygous carriers and healthy controls.

**Subject Recruitment:** This is an n=7 study. A total of seven individuals will be recruited to participate in this study. Among the participants, we will have the three affected siblings with PAPP-A2 mutation (two males and one female), their heterozygous relatives (2 parents) and 2 healthy adult controls. We will have a thorough conversation with them about the risks and benefits of participating in this study. Written informed consent will be obtained. The affected subjects and family members will all be recruited directly by [name]. They have already participated in the initial research protocol which identified the genetic defect. Each family member will be allowed to decide for themselves whether they wish to participate and it will not be necessary for all family members to participate in order to proceed with the study. All travel costs and accommodations will be covered by the Cincinnati Center for Growth Disorders. No additional compensation will be given to the subjects or their family members.

**Recruitment of controls:** 2 healthy adult controls (one male and one female) between the ages of 18-30 will be recruited from community and/or university advertising. Additionally, one of the co-investigators who meets all eligibility criteria will act as the female control subject. In order to be included in our study, the volunteers will have to be between the ages of 18-30, be in good general health and not taking any medications (with the exception of contraceptives). The candidates will have an initial screening visit in the outpatient CTRC where they will undergo full physical examination. Additionally, the following fasting labs will be obtained: CBC, renal profile, lipid profile, HgbA1C, insulin, IGF-1, IGFBP-3, random growth hormone, and urine pregnancy test (which will be repeated prior to starting the study). Any abnormal lab results or physical exam finding will result in exclusion from the study. The subjects will be informed of any abnormal lab results. They will be contacted via telephone and will receive a copy of the lab results. In addition, they will be referred to their PCP for further evaluation and treatment (if needed). We will have a thorough conversation with them about the risks of participating in this study. Written informed consent will be obtained. Volunteers will be paid \$500 upon completion of all study procedures.

**Study Protocol:** The patients, their heterozygous relatives and the healthy controls will come to the outpatient clinical translational research center (CTRC) on the morning of the study. They will be told to fast after midnight the prior evening. An indwelling venous catheter will be placed. A urine pregnancy test will be obtained from all females participating in our study. Baseline levels for IGF-1, free IGF-1, IGFBP-3, IGF-1 bioactivity, GH and blood glucose will be obtained between 8-9 AM. At 9:00 h a single injection of rhIGF-1 (mecasermin, Increlex®) will be administered at a dose of 120 mcg/kg. This dose was chosen in order to be able to compare to the study performed by [name] as mentioned in the preliminary data. Breakfast will be provided immediately after the SC injection of rhIGF-1. Blood samples for GH, IGFBP-3, IGF-1, free IGF-1, IGF-1 bioactivity and blood glucose will be repeated every 30 minutes, then every hour, every two hours until 9 PM. Subjects will then be sent home and a final sample will be drawn at 9 AM the following morning (a 24 hour time point) as detailed below. Approximately 5 ml of whole blood will be drawn per sample. The total amount of blood for this study is less than 5% of the blood volume for the youngest subject. Additionally, blood glucose monitoring (by finger stick glucose measurement) will be available as needed for symptoms of hypoglycemia.

[figure not shown]

Figure 1

#### 4.2. Prolonged rhIGF-1 treatment:

This phase of the study, will serve as a proof of principle to demonstrate that subcutaneous administration (via 2 injections daily) of rhIGF-1 is effective in improving the growth velocity in patients with PAPP-A2 mutation. The FDA-approved dosing regimen will be applied to these patients during the entire treatment period.

**Subject recruitment:** This is an n=2 study. The two youngest male siblings with PAPP-A2 mutation will participate in this protocol. We will have a thorough conversation with them and with their parents about the risks and benefits of participating in this study.

**Study Protocol:** Our patients will be given twice daily SC injections of rhIGF-1 (Mecasermin, Increlex®) longitudinally first for a period of one year. To assess the effectiveness of the treatment, the height velocity in our patients will be compared to their pre-treatment data which is available from our previous

measurements. The patients will come to the CCHMC CTRC for a series of outpatient research visits. The lab and assessment schedule is detailed below.

On day 1, the patients will present to the outpatient CTRC. They will undergo a full physical examination with close attention to pubertal staging. ECG will be performed. Baseline height in triplicate (cm) and weight (Kg) will be measured using a wall-mounted Harpenden stadiometer and electronic scale respectively. During this visit, fasting blood samples will be obtained in addition to further testing including DXA scan, pQCT and US as detailed in section 4.3.

Following the initial PK study at CCHMC, the patients will then undergo a one-year treatment trial with rhIGF-1 which will be started at 60 mcg/kg BID SC given twice daily for one week. If well tolerated, the IGF-I will be increased to 120 mcg/kg BID SC and the patients will be maintained at this dosage for one year. Doses will be given within 20 minutes of eating breakfast and dinner. Tolerability will be determined with frequent blood glucose measurements via finger stick. The patients will be instructed to measure their blood glucose 3 times per day: fasting, between 10:00-12:00 h, and between 20:00-22:00 h. In addition, they will keep a daily log which we will review via telephone or e-mail. Once the dose is increased to 120 mcg BID, they will continue to measure their blood glucose for one additional week. If no significant episodes of hypoglycemia occur, then they can continue to measure their blood glucose only as needed for symptoms of hypoglycemia. If hypoglycemia dose occur, the parents will be instructed to treat the patient with fast acting carbohydrates (such as juice) and to recheck the blood sugar in 15 minutes as we do with our patients with type 1 diabetes.

They will be re-evaluated as outpatients after 3 months, 6 months, 9 months and 12 months of treatment for serial height measurements and for close monitoring of possible side effects. The dose of rhIGF-I will be adjusted for weight at each of these visits. ECG will be performed at baseline and at each of the study visits. Echocardiogram will be performed at the 6 month and 12 month visit. A funduscopic, oropharyngeal, back and hip exam will be performed at baseline and during each of the study visits. A glucometer and testing strips will be provided for home monitoring of blood glucose concentration. We will have monthly follow up calls with the family to assess for any complications. In addition, we will be in close contact with the patient's primary care provider and local endocrinologist who will receive a detailed letter after each of the follow up visits. If any unexpected issues arise we will help coordinate prompt follow up with PCP or with local endocrinologist.

Study drug is being donated by Ipsen (the drug manufacturer) and will be provided to the patients by the study team at no cost.

**Dosage Interruption** – In the event that either participant experiences a dosage interruption of >48 consecutive hours during the one year trial, the participant will be restarted at a dose of 60 mcg/kg BID SC given twice daily for one week. If well tolerated, the IGF-I will be increased to 120 mcg/kg BID SC and the patient will be maintained at this dosage for the remainder of the one year trial.

#### 4.3. Additional phenotypic description of patients with PAPP-A2 mutation.

This part of our study will investigate further phenotypic characteristics of patients with *PAPPA2* mutations including glucose handling, body composition, bone geometry and density and renal/spleen size.

**Subject recruitment:** This is an n=3 study. We will perform this testing on all 3 affected siblings at baseline. We will then repeat this testing in the two siblings who are undergoing IGF-1 therapy at the 1 year time point. If either of the siblings stops the IGF-1 therapy prior to the completion of the 1 year trial, the below testing (as shown in table 1 and figure 2 below for 12 months) will still be completed at the 1 year time point for both siblings.

**Study protocol:** In order to achieve this, the following tests will be performed in all three siblings affected by the PAPP-A2 mutation:

- **Dual energy-x-ray absorptiometry (DXA):** bone mineral content (BMC), bone mineral density (BMD), fat-free mass (FFM), and estimates of percent body fat will be measured using DXA scans of total body, lumbar spine, hip and forearm. DXA scans will be acquired using the Hologic Discovery and standard positioning as described by the manufacturer. Scans will be analyzed using software Apex 4.0. To avoid the size-related DXA artifacts typical of individuals with short stature, age- and gender-specific results will be corrected for body size.
- **Peripheral quantitative computed tomography (pQCT):** pQCT scans will be obtained on the tibia at the distal 3%, 38% and 65% sites. The tibia at the 3% site is within the distal metaphysis and is composed primarily of trabecular bone. The tibia at the 38% site is located in the diaphysis and is predominantly composed of cortical bone. Additionally, the tibia at the 65% site provides information about the relationship between bone and muscle mass. pQCT scans will be acquired using the Stratec XCT 2000 scanner with a voxel size of 0.4 mm and a speed of 25 mm/sec. Scans will be analyzed with software version 5.50. Outcome variables analyzed will include trabecular and total volumetric BMD at the distal radius as well as cortical density and thickness, BMC, muscle area and the ratios BMC to muscle and cortical to total cross-sectional area at the distal radius.
- **Bone age:** Standard left hand and wrist X rays will be obtained to assess bone age using the Greulich–Pyle Atlas.
- **Renal and spleen ultrasound:** IGF-1 plays an important role in organ growth and some patients treated with IGF-1 therapy have been noted to have more rapid growth of the kidneys and spleen, especially during the first 2-3 years of their therapy
- **Oral glucose tolerance test**
- **Potential development of antibodies to administered rhIGF-1**

Table 1

Lab and assessment schedule:

[figure not shown]
Lab	Day 1	3 Months	6 Months	9 Months	12 Months
CBC	X				X
Metabolic Panel*	X	X	X	X	X
Lipid Profile	X				X
OGTT	X				X
A1C	X		X		X
Insulin	X	X	X	X	X
Glucose	X	X	X	X	X
GH	X	X	X	X	X
IGF-I	X	X	X	X	X
IGFBP-3	X	X	X	X	X
ALS	X	X	X	X	X
Free IGF-I	X	X	X	X	X
PAPP A2	X	X	X	X	X
rhIGF-I Antibodies	X	X	X	X	X
Osteocalcin					X*
C-telopeptide					X*
Additional Testing:					
DXA scan	X				X*
ECG	X	X	X	X	X
Echocardiogram			X		X
pQCT	X				X*
Bone age	X				X*
Renal US	X				X*
Spleen US	X				X*

\*Comprehensive Metabolic panel includes: Electrolytes, BUN, Creatinine, Calcium, Glucose, Albumin, Total Protein, AST, ALT, ALP (Alk Phos), and Total Bilirubin

\*This testing will only be repeated in the patients with PAPP-A2 mutation who received rhIGF-1 treatment.

### Timeline of the study:

Figure 2

### 5. Available and Needed Resources

Investigators will use the CTRC for admitting and following up the patients. The CTRC core laboratory and the endocrinology laboratory will be used to measure most of the laboratory parameters noted above. Some specialized samples including free IGF-1 and IGF-1 bioactivity will be analyzed either in [name] or in one of our collaborator's laboratory.

## 7. Statistical Analysis

The one-year trial with rhIGF-1 in two patients with PAPP-A2 mutation is a descriptive study which will not have a formal statistical analysis. We will describe the changes in growth velocity, height SDS, bone mineral density and other biochemical parameters, but formal statistical analysis will not be performed.

A non-compartmental analysis will be performed on the total IGF-1 concentrations and free IGF-1 concentrations to assess the PK parameters:  $C_{max}$ ,  $t_{max}$ ,  $AUC_{0-24h}$ , and  $AUC_{0-12h}$  with and without IGF-1 baseline correction. A non-compartmental analysis will be also performed on the IGFBP-3 concentrations to assess the following parameters:  $C_{max}$ ,  $t_{max}$ ,  $AUC_{0-24h}$ , , and  $AUC_{0-12h}$  with and without IGFBP-3 baseline correction. All results will be presented as summary measures with confidence intervals as well as graphical displays for the affected individuals, the heterozygous relatives and the two healthy controls as three separate groups.

## 9. Risks/Benefits.

The main benefit expected from this study is to improve the linear growth of the two young males affected by the PAPP-A2 mutation. In addition, this study will contribute to a better understanding of the recently described PAPP-A2 mutation and potential co-morbidities as well as treatment options for affected individuals.

RhIGF-1 side effects: The major risks from this trial are related to the treatment with rhIGF-1 (Increlex®) itself. Known side effects of this FDA-approved medication include hypoglycemia, hypersensitivity (allergic reactions), intracranial hypertension, lymphoid tissue hypertrophy (which can include tonsillar hypertrophy), slipped capital femoral epiphysis (SCFE) and progression of scoliosis, echocardiographic evidence of cardiomegaly/valvulopathy without associated symptoms, liver

dysfunction, alopecia, osteonecrosis, systemic hypersensitivity, and potential initiation and progression of malignant tumors. Our patients will receive their initial dose of rhIGF-1 in a controlled setting and they will be closely monitored for the development of any of these adverse effects.

- Hypoglycemia: The patients will receive a glucometer for blood glucose monitoring at home. They will be instructed to measure their blood glucose regularly during the first 2 weeks of treatment. If no significant episodes of hypoglycemia occur, they can continue to measure their blood glucose only as needed for signs or symptoms of hypoglycemia.
- Intracranial hypertension: A funduscopic exam will be performed at baseline and at each follow up visit. In the case of persistent headache +/- blurred vision or vomiting, the patient will be referred to a local ophthalmologist for dilated eye exam in order to rule out papilledema.
- Lymphoid hypertrophy: Tonsillar hypertrophy will be assessed clinically at baseline and at each follow up visit.
- SCFE: A hip exam will be performed at baseline and at each follow up visit. If the patient develops hip or knee pain at any time during the study a hip X-ray will be obtained in order to rule out SCFE.
- Cardiomegaly/valvulopathy: ECG will be done at baseline and all study visits; echocardiogram will be performed at 6 months and 12 months visits
- Liver dysfunction: a comprehensive metabolic panel will be performed at baseline and each study visit
- Development of malignant neoplasia: If malignant neoplasia develops in any patients receiving Increlex therapy, treatment will be immediately discontinued and the patient will be referred for the appropriate medical care.

In addition, we will be in close contact with the patient's primary care provider and local endocrinologist who will receive a detailed letter after each of the follow up visits. If any unexpected issues arise we will help coordinate prompt follow up with PCP or with local endocrinologist.

**Injection site reactions:** The patients can experience local symptoms related to the subcutaneous administration of rhIGF-1 which include pain at the site of the injection, redness, small bruising, lipoatrophy or lipohypertrophy. Injection site reactions can be avoided by changing the injection site at each injection (injection site rotation).

**Immunogenicity:** There is a risk of potential development of antibodies to administered rhIGF-1. Blood samples will be taken at baseline, periodically and at the end of the study to monitor the potential generation of antibodies.

**Radiation risk:** Every person is exposed on a daily basis to a certain amount of background radiation originating from soil, rocks, outer space and within the body itself. The amount of radiation for imaging studies varies based on the size of the patient, with children and smaller adolescents being exposed to relatively larger doses of radiation than adults. The average person in Cincinnati receives a radiation dose of about 3 mSv per year. Using the largest exposure estimates for children, the proposed radiology studies would expose the patients to the following amounts of radiation:

- DXA scan (total body, lumbar spine, hip and forearm): 0.013 mSv; two DXA scans: 0.027 mSv
- peripheral QCT: less than 0.01 mSv; two peripheral QCT: less than 0.02 mSv
- Bone age (X-ray of the hand): 0.005 mSv; two bone age studies: 0.01 mSv

Therefore, total radiation exposure from this study is expected to be 0.05 mSv or less (equivalent to the amount an individual receives over 6 days from background radiation).

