The three affected siblings (two males, one female), will be assessed at the yearly outpatient study visits for further phenotyping. During this visit, we will obtain fasting blood samples in addition to the following tests:

- Oral glucose tolerance test (OGTT)
- Dual energy-x-ray absorptiometry (DXA) scan of whole body, lumbar spine, hip and forearm.
- The two affected brothers that are still growing will get a repeat bone age x-ray.
- The affected younger brother on rhIGF-I treatment will have an electrocardiogram, and repeat renal and spleen ultrasounds. (Please refer to the original protocol for full details).

These tests were all done at baseline and at the end of the first year of the trial as well. Since this has already been approved, we have not included it in the extension trial application or protocol.

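### Do the listed scan doses contradict the stated radiation total of 0.05 mSv, and does the extension need a new one?

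*Combined protocol and SAP*

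**What the plan says.** Section 9 of the main protocol, under radiation risk, puts background in Cincinnati at about 3 mSv per year and introduces its dose list with the phrase "Using the largest exposure estimates for children". The entries are:

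- DXA: 0.013 mSv for one scan session and 0.027 mSv for two.
- "peripheral QCT: less than 0.01 mSv; two peripheral QCT: less than 0.02 mSv"
- Hand film for bone age: 0.005 mSv for one and 0.01 mSv for two.

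It then concludes: "Therefore, total radiation exposure from this study is expected to be 0.05 mSv or less", which it equates to 6 days of background.

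Two of each scan is the right count for the treated brothers. Section 4.3 tests all three siblings at baseline and adds: "We will then repeat this testing in the two siblings who are undergoing IGF-1 therapy at the 1 year time point". Table 1 agrees, with DXA, peripheral QCT and bone age on Day 1 and at 12 months.

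The extension (section headed Study protocol, and its assessment schedule) keeps a yearly "Dual energy-x-ray absorptiometry (DXA) scan of whole body, lumbar spine, hip and forearm" and a bone-age film for siblings still growing. It has no peripheral QCT. Extension section 8 says only that the risks and benefits have not changed.

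**The concern.** The list is presented as maximum estimates, and the total is presented as its consequence and as an upper limit. A reader who adds the entries gets a number above 0.05, so the conclusion looks like an addition error in a safety statement about young participants.

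The extension seems to make this worse. It schedules further DXA scans and bone-age films, while its risk section refers back to the main protocol without a new total. If 0.05 mSv were taken to cover the whole period of participation, it would be too low for a growing brother from the first extension phenotyping visit onward. What would be at stake is the accuracy of a risk description, and so possibly what families are told.

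**Working it through.** **Inputs** (section 9, mSv): DXA 0.013 each, 0.027 for two; peripheral QCT below 0.01 each, below 0.02 for two; bone age 0.005 each, 0.01 for two; background 3 per year.

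**The plan's own conversion.** Days of background = dose / 3 × 365. For 0.05: 0.05 / 3 × 365 = 6.1 days. The stated 6 days therefore agrees with the stated 0.05.

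**One-year sum, treated brother.** 0.027 + (<0.02) + 0.01 = <0.057 mSv, and 0.057 / 3 × 365 = 6.9 days. With DXA taken as 2 × 0.013 = 0.026, the sum is <0.056 mSv, or 6.8 days. The 0.026 against 0.027 is consistent with rounding: 0.0133 rounds to 0.013, and 2 × 0.0133 = 0.0266 rounds to 0.027. Neither sum gives 0.05 as a ceiling.

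**Can 0.05 still be true?** DXA and bone age contribute 0.027 + 0.01 = 0.037. The remainder is 0.05 − 0.037 = 0.013 for two peripheral QCT scans, or 0.0065 each. With DXA at 0.026 the allowance is (0.05 − 0.036) / 2 = 0.007 each. The document says only that each is below 0.01, so a true total at or under 0.05 is compatible with the list but not guaranteed by it.

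**Size of the gap.** At most 0.057 − 0.05 = 0.007 mSv. This is 14% of the stated figure and 0.007 / 3 × 365 = 0.85 day of background.

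**Sister.** With one set of scans, as in section 4.3: 0.013 + (<0.01) + 0.005 = <0.028 mSv, inside the stated total.

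**Extension.** Each yearly visit adds 0.013 mSv for DXA alone, or 0.013 + 0.005 = 0.018 mSv with a bone-age film. The larger figure is 0.018 / 3 × 365 = 2.2 days of background. For a brother still growing at month 24:

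- DXA and bone age only: 0.037 + 0.018 = 0.055 mSv.
- Upper bound with the first-year peripheral QCT: <0.057 + 0.018 = <0.075 mSv, or 9.1 days.

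The first line exceeds 0.05 whatever the peripheral QCT dose. However, it is a two-year accumulation, and the 0.05 in section 9 was built from two sets of scans in the one-year study. Year for year, the extension adds 0.018 mSv or less, about a third of the one-year figure (0.018 / 0.05 = 36%).

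**The case for a change.** The strongest case for a change is that the sum can be checked from the list alone. With maximum estimates as inputs, the words linking list and total invite the reader to treat 0.05 as a guaranteed limit, and it is not one. The extension point is firmer still, because DXA and bone age alone pass 0.05 by month 24 and no cumulative figure appears in the available extension text. The correction would be cheap, and the participants include minors.

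The arithmetic stands. As a proven ceiling, 0.05 is unsupported, and a cumulative extension dose is not written down in the text at hand. Three things limit its force.

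- The sentence states an expectation, and the list permits it to be true. No exceedance in the one-year part has been shown.
- The extension section does not repeat 0.05. Saying that the risks have not changed can reasonably mean that the kinds of risk are the same: DXA and hand films are procedures already described, with a dose for each. Anyone needing a running total can add 0.013 or 0.018 mSv per visit, as above.
- The separate extension consent and assent, and the text before extension section 2, were not available. The absence of a cumulative figure can be asserted only for the text that was.

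**Conclusion.** No change to the plan follows. The one-year statement is loose by at most 0.007 mSv, under a day of background, and holds if each peripheral QCT delivers 0.0065 mSv or less. The extension leaves a sum undone that the listed per-scan doses let any reader complete: 0.013 to 0.018 mSv per yearly visit, at most about 2.2 days of background.

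Nothing the trial does or concludes rests on either number. Section 7 describes the treatment part as descriptive, without formal analysis. No eligibility, withdrawal or completion rule refers to radiation dose, and the imaging schedule would be the same with the total written as 0.05 or 0.06. Section 4 reports the one-year part as complete, so rewording its total would affect no future scan. It also says of the phenotyping: "This part will be complete in 2019 for the subjects not on Increlex". The extension increment therefore concerns mainly the treated brother.

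This conclusion assumes that the listed doses are the upper estimates the protocol says they are, and that the treated brothers had two sets of scans in the first year. It takes no position on the wording of the consent and assent, which were not available.
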